The anesthesia provider will be readily available to assess the patient during her labor and delivery per our standard practice. As per our standard practice, the anesthesia provider will evaluate the patient within 24 hours after delivery to assess for any complications.

Providers: If at any time the anesthesia provider feels uncomfortable or incapable of using the randomized technique to identify midline, he or she will be removed from the study. They will be allowed to freely choose their technique of choice in identifying midline. If this occurs, the participating patient in the study will be informed that she is no longer randomized and will be removed from the study. The patient will still receive standard of care treatment as described above.

At the mid-point of the study, our results will be reviewed by our statistician and if there is a highly significant result in either group, the study will be discontinued due to the overwhelming benefit of either palpation or ultrasound. Since patients are only recruited for the study the day of their epidural, no patients will need to be contacted if the study is discontinued.

- c. If hazards occur that might make the risks of participation outweigh the benefits for all participants, describe (i) the criteria that will be used to stop or end the entire study and (ii) any special procedures, precautions, or follow-up that will be used to ensure the safety of currently enrolled participants.

After a significant number of patients have been enrolled, we will perform a preliminary analysis of the data. If the data suggests there is a strongly significant benefit (or harm) to a certain group, such as much prolonged time in placement or a significantly improved success rate, we will end the study. Since patients are only enrolled in the study during their labor and delivery (as opposed to prolonged follow-up), there should be no special precautions that would need to be taken. Recruitment would just end due to the study ending.

20. Informed Consent

The answers below pertain to the patient participants. We are asking for a waiver of informed consent for the provider participants.

- a. Do you plan to obtain informed consent for this protocol? Yes No
If Yes, complete the items below.

If No, complete and include the Waiver of Informed Consent or Waiver of Authorization and Informed Consent, as applicable.

- b. Do you plan to document informed consent for this protocol? Yes No
If Yes, complete the items below.

If No, complete the items below **and** include the Waiver of Informed Consent Documentation.

- c. How will consent be obtained? Once a potential candidate is determined, PI or a co-investigator will discuss the study with the patient in a private setting and allow for any questions. Once the study is explained and all questions are answered, informed written consent will be obtained by the PI or co-investigator before any obstetric intervention occurs that might cause pain or altered mental status to the patient.

- d. Who will conduct the consent interview? PI or a co-investigator.

- e. Who are the persons who will provide consent or permission? The participant.

- f. What steps will be taken to minimize the possibility of coercion or undue influence?
All patients will be approached the day of admission in accordance with our current practice. If patients are experiencing extreme pain because of contractions, they will not be approached for the study.

- g. What language will the prospective participant or the legally authorized representative understand? English
- h. What language will be used to obtain consent? English
- i. If any potential participants will be, or will have been, in a stressful, painful, or drugged condition before or during the consent process, describe the precautions proposed to overcome the effect of the condition on the consent process. If not, enter "no such effect."
No such effect
- j. If any project-specific instruments will be used in the consenting process, such as flip charts or videos, describe the instrument(s) here, and provide a copy of each. If not, enter "not used."
Not used
- k. How long will participants have between the time they are told about the study and the time they must decide whether to enroll? If not 24 hours or more, describe the proposed time interval and why the 24-hour minimum is neither feasible nor practical. The 24-hour minimum will not be feasible or practical for this study, since the time between admission for induction of labor and placement of a labor epidural will be less than 24 hours. Therefore, we will begin the consent process when the patient has arrived on the Labor and Delivery floor.

21. Procedures to Protect Privacy

Describe the provisions included in the research to protect the privacy interests of participants (e.g., others will not overhear your conversation with potential participants, individuals will not be publicly identified or embarrassed).

Patients: All patients will be recruited through direct and private interview with them by either the PI or co-investigator. They will read the informed consent document explaining the research project. All questions and concerns will be answered.

Providers: Anesthesia provider data will have no personal identifying markers except for training level.

22. Procedures to Maintain Confidentiality

- a. Describe the manner and method for storing research data and maintaining confidentiality. If data will be stored electronically anywhere other than a server maintained centrally by UAB, identify the departmental and all computer systems used to store protocol-related data, and describe how access to that data will be limited to those with a need to know.

Patient data will be gathered through direct interview with the patient and through secure password-protected online medical records. Anesthesia provider data will have no personal identifying markers except for training level. Also the times as discussed above will be documented. Data will initially be collected on paper and will be kept in a locked filing cabinet in the locked office of the PI. The paper data records will be transferred to a secure password-protected research drive maintained by the Department of Anesthesiology. The research drive is HIPAA compliant and has researcher specific restricted access. This research server is backed up to another secure research server at a different location.

- b. Will any information derived from this study be given to any person, including the subject, or any group, including coordinating centers and sponsors? Yes No
If Yes, complete i-iii.

- i. To whom will the information be given? Information will be shared with the UAB Anesthesiology faculty and residents and other entities within the UAB Health System for quality improvement. Information may be presented at scientific meetings, conferences, or may be published.
- ii. What is the nature of the information? Findings from study. Information regarding participant demographics will only be presented in aggregate form – age, sex, race, differences in pre-existing medical conditions, and variables in procedure management.
- iii. How will the information be identified, coded, etc.? Information will be de-identified and will be presented in aggregate form. None of the 18 HIPAA identifiers will be disclosed.

23. Additional Information

In the space below, provide any additional information that you believe may help the IRB review the proposed research, or enter "None."

None

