Note. Codes are not identifying as long as the researcher cannot link the data to an individual

- None—**If None, skip to Item 13.**

e. Choose one plan to describe your use of the personal health information:

- The data collected meet the specifications for a "limited data set"
—Attach Data Use Agreement or Business Associate Agreement
- Research staff will obtain authorization from each patient to use the information
—Attach Patient Authorization form, complete except for patient name and IRB protocol number
- PI requests Waiver of Patient Authorization to use the information
—Attach Waiver of Authorization and Informed Consent form

PROPOSED RESEARCH

- The IRB will not accept grant applications and/or sponsor's protocols in lieu of the items as outlined below.
- Do not separate responses from items. Instead, insert your response to each item below the item, keeping the information in the order of this form.
- Number each page of the Human Subjects Protocol (i.e., Page X of Y).

13. Purpose—in nontechnical, lay language

Summarize the purpose and objectives of this protocol, including any related projects, in one short paragraph.

This study will address the utility of ultrasound in the placement of an epidural catheter in severely obese parturients. Identification of midline can often be difficult using the standard method of palpation in obese patients. We will determine if the use of ultrasound decreases the amount of time and number of attempts required to place the epidural.

The study will be conducted on the labor and delivery unit at the Women and Infants' Center. Participants will include laboring parturients who request an epidural. Inclusion criteria: patient request for an epidural and a diagnosis of severe obesity (BMI \geq 35). Exclusion criteria: BMI $<$ 35, patient refusal of a labor epidural, coagulopathy, platelets $<$ 80,000, prior spine procedure or instrumentation, a diagnosis of scoliosis, and an intracranial or spinal mass. The primary outcomes for the study will be time required to locate midline of the back using ultrasound or palpation and time required for epidural placement. The secondary outcomes for the study will be (1) number of attempts or passes required for placement, (2) epidural failure rate, and (3) time difference between provider groups (junior resident, senior resident, attending).

14. Background—in nontechnical, lay language

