Summarize in 2-3 paragraphs past experimental and/or clinical findings leading to the formulation of this study. Include any relevant past or current research by the Principal Investigator. For drug and device studies summarize the previous results (i.e., Phase I/II or III studies).

The use of ultrasound has expanded into many areas of medicine including the identification of bony landmarks to facilitate epidural placement in obstetric anesthesia. Using ultrasound for epidural placement has become popular over the last decade with several studies being published on the topic. The likely increase in popularity for ultrasound use in the obstetric population is the need to more reliably locate bony landmarks as the traditional palpation technique has been shown to be an inaccurate way to accomplish this. One study reports that only 55% of the documented interspinous spaces during neuraxial anesthesia were correctly identified by palpation.

There have been several articles reporting the use of ultrasound in neuraxial anesthesia but none identifying its utility in the obese population. In patients with BMI $<$ 35 or those who have easily palpable spines, there is no statistical difference in number of attempts or patient satisfaction. In other studies where there were no limitations on BMI, there was a significant difference in number of attempts, patient satisfaction, successfulness of the block, and occurrence of dural puncture with the use of ultrasound. One study reports that these results are even more significant in resident trainees. In this study, investigators evaluated the use of ultrasound scanning by first year residents and found that identification of midline and measurement of the depth of the epidural space significantly decreased the number of attempts required and decreased the epidural failure rate.

Given the fact that the long-taught palpation technique can be inaccurate and studies have validated the use of ultrasound for epidural placement, ultrasound technique is routinely taught by the obstetric anesthesiologists to the anesthesiology residents at UAB. Also, since both techniques are considered standard practice at UAB, anesthesia providers (residents, fellows, and faculty) are free to choose either technique to locate bony structures of the back prior to epidural placement. Since no current study has specifically addressed its use in the obese pregnant patient, we would like to validate its use in this population.

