Eligibility Criteria: patient request for a labor epidural, BMI ≥ 35 . Eligibility criteria for anesthesia providers include those providers trained in both epidural placement and use of ultrasound for epidural placement.

Exclusion Criteria: BMI < 35 , patient refusal of a labor epidural, coagulopathy, platelets $< 80,000$, prior spine procedure or instrumentation, a diagnosis of scoliosis, and an intracranial or spinal mass. Exclusion criteria for anesthesia providers: those not trained in epidural placement or use of ultrasound for epidural placement.

- d. If participants will comprise more than one group or stratification, describe each group (e.g., treatment/intervention, placebo, controls, sham treatment) **and** provide the number of participants anticipated in each group.

Patient Participants: There will be a total of 150 participants randomized into two groups: palpation group (P) and ultrasound group (U). The randomization will be a 1:1 randomization. The technique will be chosen by randomly drawing a sealed envelope from a box that will contain a card with either palpation or ultrasound written on it. The palpation group will have an epidural placed after manual palpation of the spine. The ultrasound group will have an epidural placed after identifying midline with the ultrasound. There are no placebo or sham treatment groups. There will be no randomization of anesthesia provider. Any available anesthesia provider (if eligible to participate in the study) will place the epidural.

Provider Participants: Since we will continue with our standard practice of epidural placement, all providers trained in both ultrasound use and epidural placement will be able to place the epidural. This process will not be randomized. Providers will be chosen based on availability (i.e. if a patient requests an epidural at the time only one qualified provider is available, then that provider will place the epidural) or patient request (i.e. if a patient requests a certain qualified provider by name or level of training such as a fellow or faculty request). The provider training level will be documented on the data sheet.

e. Indicate which, if any, of the special populations listed below will be involved in the protocol. Include the Special Populations Review Form (SPRF) if indicated.

Pregnant Women: Attach SPRF—Pregnant Women, Fetuses, Neonates/Nonviable Neonates

Fetuses: Attach SPRF—Pregnant Women, Fetuses, Neonates/Nonviable Neonates

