The IMPACT Labor & Delivery Room list will be used to identify potential participants.

- i. Describe the procedures for screening potential participants.

Once a patient is admitted to the labor and delivery suite, we will review their medical record to see if she is eligible to participate by meeting the above inclusion/exclusion criteria. Once this is determined, we will then discuss the study with the patient and obtain informed, written consent if they choose to participate.

16. Protocol Procedures, Methods, and Duration of the Study—in nontechnical language

- a. Describe the study methodology that will affect the participants—particularly in regard to any inconvenience, danger, or discomfort.

Providers: All investigators involved in this study have received training in use of the ultrasound for epidural placement and use the ultrasound in routine practice. Prior to being allowed to participate in the study, the anesthesia provider must demonstrate proficiency in the use of ultrasound. This will be accomplished on our obstetric anesthesia simulation model. Patients: Once informed consent is obtained, participants in the study will be randomized to either have the midline of their back located by ultrasound (U) or by palpation (P). After midline is located, the epidural catheter will be placed in routine fashion. Providers: Each provider will be timed on two events during epidural placement: (1) from start to completion of ultrasound exam/palpation exam and (2) from local injection of lidocaine at the skin to injection of the test dose. The primary outcomes for the study will be time required to perform the ultrasound/palpation exam of midline and time required for epidural placement. The secondary outcomes for the study will be (1) number of attempts or passes (defined as the need to remove the needle to the skin and redirect towards the epidural space) required for placement, (2) epidural failure rate (defined as inability to achieve a T10 level after 1 hour of epidural infusion and at least 10 mL of a local anesthetic bolus), and (3) time difference in provider level (junior resident, senior resident, attending).

- b. What is the probable length of time required for the entire study (i.e., recruitment through data analysis to study closure)?

1 year

- c. What is the total amount of time each participant will be involved?

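### Obesity is the reason for the trial, but BMI is used only as an entry cut-off, with no stated plan to keep the value, adjust the primary times for it, or describe the effect above 35

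*Combined protocol and SAP*

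**What the plan says.** Item 13 (Purpose) gives the motive: the midline is often hard to find by palpation in obese patients. Item 14 (Background) contrasts two bodies of evidence. For the first, "In patients with BMI $<$ 35 or those who have easily palpable spines, there is no statistical difference in number of attempts or patient satisfaction". For the second, "In other studies where there were no limitations on BMI, there was a significant difference in number of attempts, patient satisfaction, successfulness of the block", among other outcomes. It adds that the obese pregnant patient has not been studied specifically.

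BMI then enters the design once, as a threshold in item 15.c: "Eligibility Criteria: patient request for a labor epidural, BMI ≥ 35". There is no upper limit. It is read from the chart before enrolment, since under item 15.i "we will review their medical record to see if she is eligible to participate by meeting the above inclusion/exclusion criteria".

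Allocation (item 15.d) is 1:1 among 150 patients, and "The technique will be chosen by randomly drawing a sealed envelope from a box that will contain a card with either palpation or ultrasound written" (sentence shortened). No stratification is mentioned. Item 13 names two times as primary, one to find the midline and one to site the catheter: "The primary outcomes for the study will be time required to locate midline of the back using ultrasound or palpation and time required for epidural" (sentence shortened). Only one breakdown is planned, in items 13 and 16.a, and it is by provider level. Item 22.b.ii lists the participant information to be presented and does not name BMI. No statistical method or covariate is stated for any outcome.

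**The concern.** A patient characteristic that motivates the trial, and is known before randomisation, is a natural baseline covariate. If it is related to the primary times, leaving it out leaves explainable variation in the error term, and the estimate is less precise than the same 150 patients could give. A reader of the results will also want to know whether the arms were alike on BMI and whether the effect looks the same across the admitted range. The plan promises neither.

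The timing of the decision matters too. With no analysis stated, BMI adjustment or a BMI cut-off could be chosen after the results are known. Settling it beforehand removes that choice.

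**Working it through.** **Inputs from the protocol:** 150 patients allocated 1:1 (item 15.d), taken as 75 per arm; two primary times (items 13 and 16.a).

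**Assumptions, none given in the protocol:** two-sided 5% test, 80% power as the reference point, no dropout, and a linear correlation r between BMI and time of 0.1 to 0.5.

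**1. The plan's own figure.** The 150 cannot be reproduced, because no alpha, power, effect size or standard deviation is stated. What it would detect is (1.960 + 0.842) × sqrt(2/75) = 2.802 × 0.163 ≈ 0.457 SD with 80% power. That effect is the reference below.

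**2. Chance BMI difference between arms.** Standard error = sqrt(2/75) = 0.163 BMI SD; 95% range = ±1.96 × 0.163 = ±0.32 SD. The chance of a difference above 0.2 SD is 22%, and above 0.3 SD it is 7%.

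**3. Effect on the estimated time difference.** Shift = r × BMI difference. At the edge of the 95% range and r = 0.3 this is 0.3 × 0.32 = 0.10 SD; at one standard error it is 0.3 × 0.163 = 0.05 SD. This is not an extra error. The unadjusted standard error already contains it, as a share r² of its square.

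**4. Gain from adjustment.** Residual SD = sqrt(1 − r²). Adjusted power = Φ(0.457 / (0.163 × sqrt(1 − r²)) − 1.96). Equivalent unadjusted total = 150 / (1 − r²).

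| r (assumed) | Shift at 95% limit (SD) | Variance removed, r² | Power, from 80% | Equivalent total |
|---|---|---|---|---|
| 0.1 | 0.03 | 1% | 80.4% | 152 |
| 0.2 | 0.06 | 4% | 81.6% | 156 |
| 0.3 | 0.10 | 9% | 83.6% | 165 |
| 0.4 | 0.13 | 16% | 86.4% | 179 |
| 0.5 | 0.16 | 25% | 89.9% | 200 |

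**5. Simulation check.** With 10,000 simulated trials at each r and a skewed BMI distribution, type I error was 5.5% unadjusted and 5.4% adjusted at r = 0.3, and 4.8% for both at r = 0.5. Power was 79% unadjusted against 82% adjusted at r = 0.3, and 79% against 89% at r = 0.5. These agree with the formula to within about 1.5 percentage points.

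**6. Variation of the effect with BMI.** The standard error of a technique-by-BMI slope is about 2/sqrt(150) = 0.163 outcome SD per BMI SD. It has 80% power only for 2.802 × 0.163 ≈ 0.46 outcome SD per BMI SD. Power is 23% for a slope of 0.2 and 45% for 0.3. Splitting BMI at the median would need the two subgroup effects to differ by (1.960 + 0.842) × sqrt(4/37.5) ≈ 0.91 SD.

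**The case against.** The strongest reply is that this is a small symptom of a larger gap. No analysis is given for any outcome, so the plan does not commit to an unadjusted comparison. The data sheet is mentioned but not reproduced, so BMI may be among its fields. No BMI–time correlation is given, and restricting entry to 35 or more would tend to weaken one. Exam time in one arm is an ultrasound scan, for which the documents suggest no relation to BMI. All of this stands. It is why the point concerns what is unstated, and why the low values of r belong in the table. It does not dispose of the point: supplying a generic method such as a t-test would still leave BMI out.

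Three stronger readings are tempting, and the documents do not support them.

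- A reader might infer that the plan treats BMI as governing whether ultrasound helps, with benefit rising as obesity increases. Item 14 only contrasts separate studies, pairs low BMI with easily palpable spines, and in neither contrast mentions time. Nothing is said about a gradient above 35, and a simple threshold fits the stated rationale.
- A reader might infer that chance BMI imbalance distorts the comparison. It can move a single estimate, but randomisation makes it neither bias nor a source of false positives, as step 5 shows. The shift and the wider interval are the same phenomenon and should not be counted twice.
- A reader might infer that the trial cannot show how the effect varies with BMI. If the value is kept, it can be examined. What the documents support is that no such analysis is planned and that 150 patients would detect only a large variation.

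**Conclusion.** The point holds as one of precision and prespecification, not validity. BMI motivates the trial and is available before randomisation, but its only stated use is the cut-off at 35.

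The cost of leaving it out lies between negligible and useful. Adjustment lifts 80% power by 0.4 to 1.6 points at r = 0.1 to 0.2, and by about 4 to 10 points at r = 0.3 to 0.5. The upper range is the favourable end; the documents do not place r within it, and r may differ between the two primary times. The figures also assume 75 analysed per arm and a two-sided 5% test. The change is worth making because it is nearly free.

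**What to change.** - Enter the BMI used for eligibility on the data sheet, as a number, before the envelope is opened.
- Tabulate BMI by arm.
- State in advance that both primary times will be compared with continuous BMI as a baseline covariate, on the log scale if the times are skewed.
- Optionally, report the technique-by-BMI slope with its confidence interval, labelled exploratory, and note that 150 patients give 80% power only for about 0.46 outcome SD per BMI SD. Do not add a second BMI cut-off.

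The cost is one data-sheet field, one model term and a sentence or two of text, with no extra patients or procedures. The downside is that little is gained if BMI is only weakly related to time.

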15. Participants (Screening and Selection)

- a. How many participants are to be enrolled at UAB? Patient Participants: 150
Provider Participants: 80

If multi-center study, total number at all centers: N/A

- b. Describe the characteristics of anticipated or planned participants.

Sex: Female

Race/Ethnicity: All parturients in active labor

Age: 19-45

Health status: Healthy

Since we will be tracking anesthesia provider training level and times, they will also be considered as participants in this study. Each provider eligible for participation will have been properly trained in both epidural placement and use of ultrasound to place the epidural. All providers are over the age of 19 in our department, and it will be all inclusive in terms of sex and race.

Note. If data from prior studies indicate differences between the genders or among racial/ethnic groups in the proposed research or if there are no data to support or to negate such differences, Phase 3 clinical trials will be required to include sufficient and appropriate entry of gender and racial/ethnic subgroups so that trends detected in the affected subgroups can be analyzed. If ethnic, racial, and gender estimates are not included in the protocol, a clear rationale must be provided for exclusion of this information. If prior evidence indicates that the results will not show gender or racial differences, researchers are not required to use gender or race/ethnicity as selection criteria for study participants. They are, however, encouraged to include these groups. See Section II. Policy of the NIH POLICY AND GUIDELINES ON THE INCLUSION OF WOMEN AND MINORITIES AS SUBJECTS IN CLINICAL RESEARCH – Amended, October, 2001) for further details.

- c. From what population(s) will the participants be derived?

Women who are in active labor who have BMI ≥ 35 and desire a labor epidural. For anesthesia providers, participants will be from the Department of Anesthesiology at UAB and will include residents, obstetric anesthesiology fellows, and faculty.

Describe your ability to obtain access to the proposed population that will allow recruitment of the necessary number of participants:

Recruitment will be drawn from women who arrive to the UAB Labor & Delivery floor for a planned vaginal delivery. They will be the same patients who are already consented for labor epidurals.

Describe the inclusion/exclusion criteria:

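### The plan does not require the placing provider to be named before the envelope is opened, and describes no provider code to link repeat procedures when times are compared between provider levels

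*Combined protocol and SAP*

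**What the plan says.** **Allocation.** Item 15.d plans 150 patients in two arms at 1:1 and states: "The technique will be chosen by randomly drawing a sealed envelope from a box". It does not say who draws or opens the envelope, or when. Item 16.a gives the sequence: "Once informed consent is obtained, participants in the study will be randomized".

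**Timing of consent.** Items 15.e and 15.g place consent before persistent labor pain and before painful obstetric intervention. Item 20.k says "we will begin the consent process when the patient has arrived on the Labor and Delivery floor", and explains that a 24-hour decision period is not feasible "since the time between admission for induction of labor and placement of a labor epidural will be less than 24 hours".

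**Choice of provider.** Item 15.d states that providers are not randomised. They are chosen by availability ("if a patient requests an epidural at the time only one qualified provider is available", that provider places it) or by patient request ("if a patient requests a certain qualified provider by name or level of training such as a fellow or faculty request").

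**Provider data.** Item 15.d says: "The provider training level will be documented on the data sheet". Items 21 and 22.a say that provider data carry no personally identifying marker beyond training level. Item 15.a gives "Provider Participants: 80". No provider study code is described anywhere.

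**Outcomes.** Under items 13 and 16.a, both primary outcomes are times taken by the provider: the midline examination and the epidural placement. Secondary outcome 3 is the time difference across junior residents, senior residents and attendings. The plan states no analysis method for either.

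**The concern.** There are two separate gaps.

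**Order of events.** Both primary outcomes measure how fast the placing provider works. Randomisation balances provider skill between arms only if the provider is fixed before the arm is known, or is chosen without regard to it. The documents permit this order: consent, envelope, epidural request, choice of provider. The arm could then be known to whoever assigns the provider, or to a patient who may ask for a fellow or faculty member. If more experienced providers were drawn into one arm, part of the difference in times would be skill rather than technique. Provider level is recorded, so an imbalance by level would show, but skill differences within a level would not. The order of events cannot be restored once the data are collected.

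**Repeat procedures.** The same provider's times are likely to resemble each other. When times are compared between levels, each provider sits in one level, so treating that provider's procedures as independent makes the standard error too small. Without a code linking procedures to providers, no analysis of the research data can correct this.

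**Working it through.** **Inputs from the protocol:** 150 patients at 1:1 (item 15.d), so 75 per arm if exact; 80 providers (item 15.a). The documents give no SD, skill gap, provider mix, intraclass correlation (ICC) or alpha. Every other input below is an illustrative assumption, with a two-sided 5% test.

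**1. Repeats.** Minimum procedures beyond each provider's first = patients analysed − providers.
- 150 − 80 = 70, a mean of 150/80 = 1.875 procedures per provider.
- With 135 patients analysed: 135 − 80 = 55. With 120: 120 − 80 = 40. Items 18–19 of the form allow such removals (see 19.b).
- With fewer active providers the count rises: 150 − 60 = 90, and 150 − 40 = 110.

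**2. Outcome 3, levels compared with repeats ignored.** Design effect (DE) = 1 + ((CV² + 1) × 1.875 − 1) × ICC, where CV is the coefficient of variation of workload across providers. Actual type I error = 2 × [1 − Φ(1.96/√DE)].

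| Workload CV | ICC | DE | Type I error |
|---|---|---|---|
| 0 | 0.1 | 1.09 | 6.0% |
| 0 | 0.2 | 1.18 | 7.1% |
| 0 | 0.3 | 1.26 | 8.1% |
| 1 | 0.1 | 1.28 | 8.3% |
| 1 | 0.2 | 1.55 | 11.5% |
| 1 | 0.3 | 1.83 | 14.7% |

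A simulated three-level F test (80 providers split 30/30/20) gives 6 to 10% at near-equal workload and 9 to 19% at CV about 1. With ICC 0 it returns about 5%.

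**3. Primary times, if the choice of provider did depend on arm.** Assume one third of providers are experienced on average, and a gap g between levels in units of the within-level SD. Bias = difference in experienced share × g. SE = √[(1 + (1/3)(2/3)g²) × 2/75].
- Share difference 0: no bias, 5% false positives.
- 10 points, g = 0.5: bias 0.05 SD, SE 0.168, false positives 6.0%.
- 20 points, g = 1: bias 0.20 SD, SE 0.181, false positives 19.8%.

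Adjusting for level returns the rate to about 5% when selection acts only through level. A 0.10 SD shift within level survives adjustment: 0.10/√(2/75) = 0.61 standard errors, or about 9% false positives. Adjustment is therefore no substitute for fixing the order.

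**4. Precision gain from adjusting for level, with no selection.** R² = (2/9)g² / (1 + (2/9)g²).
- g = 0.5: R² = 0.053, SE ratio √(1 − 0.053) = 0.973, about 3% smaller.
- g = 1: R² = 0.182, SE ratio √(1 − 0.182) = 0.905, about 10% smaller.

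**5. Does the proposed analysis work?** In simulation under the same assumptions, a provider random intercept brings the between-level test back to about 5% at near-equal workload and 6% at uneven workload. Basic cluster-robust errors leave about 9% at uneven workload.

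**The case against.** **Nothing shows that providers are picked by arm.** This stands. Neither criterion in item 15.d refers to arm, and the item says any available eligible provider will place the epidural. Item 16.a gives a sequence, not an interval. The 24-hour figure is a ceiling for induction admissions, and item 15.c describes women in active labor, for whom the gap may be much shorter. A reader might infer that the primary comparison is biased. The documents do not support that: they only leave the route open, and the 6 to 20% range follows from assuming that selection occurs.

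**Removals under item 19.b are untouched.** This also stands. A provider who is uncomfortable with the allocated technique leaves, and the patient is removed. Naming the provider first does not prevent that exclusion. It is a separate matter, and the item describes removal, not a swap of provider.

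**Linkage may be possible.** Items 21 and 22.a exclude personally identifying markers, which does not in terms forbid a study code, and the electronic record may name the provider. But no link from that record to the research data is described.

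**Seventy is not fixed.** Correct: it requires all 150 procedures to be analysed.

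**Outcome 3 might mean the ultrasound–palpation difference by level.** A reader might take this from the remark about trainees in item 14, but items 13 and 16.a both read as a comparison of levels. Under the other reading, ignoring repeats would leave the test at about 5%, or 6 to 7% if technique effects also varied by provider.

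**Conclusion.** Both gaps are real and should be closed, but neither shows that a result will be wrong.

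For the primary times, the plan leaves open a route by which provider skill could become linked to arm. There is no bias if the choice is independent of arm, and the documents give no basis for estimating how likely dependence is.

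For secondary outcome 3, the plan as written would treat repeat procedures as independent and understate the standard error. The illustrative size is a type I error of 6 to 8% at equal workload for an assumed ICC of 0.1 to 0.3, and more if workload is uneven. This concerns one secondary outcome. The count of at least 70 repeats holds only if all 150 procedures are analysed and no more than 80 providers take part.

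Fellows are eligible under item 15.c but have no level in outcome 3, and the plan does not say whose level counts when a second provider takes over under item 19.a. A reader might infer that these omissions invalidate the outcome. They are details to clarify, no more.

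**What to change.** (a) State that the envelope is opened only after the epidural is requested and the placing provider is named and recorded.

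(b) With that order in place, adjust each primary time comparison for the level of the provider so named. Level is then a pre-randomisation covariate; without (a) it is not. The assumed gain is a standard error about 3 to 10% smaller.

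(c) Record a non-identifying study code for each provider, and analyse outcome 3 with a provider random effect.

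As clarifications, assign fellows to a level and state whose level counts after a takeover.

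**Cost.** A few lines of protocol text, one data-sheet field and some analysis wording; no extra patients. Envelopes would have to be opened at the bedside. The code may need an IRB amendment, given the wording of items 21 and 22.a and the waiver of provider consent requested in item 20. The note on codes under item 12.d does not settle this: it is form text about patient health information and covers only codes that the researcher cannot link to an individual, so a retained list linking codes to providers would fall outside it.
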